### *Study subjects*

Twenty periodontal patients of the University Hospital of Dental Prosthetics and Restorative Dentistry, Medical University of Innsbruck

Inclusion criteria:

- Completion of active periodontal treatment
- Maximum probing pocket depths of 5 mm
- No site  $\geq 4$  mm with bleeding on probing
- Bleeding on probing  $< 10\%$
- Open interproximal spaces both, in mandible and maxilla
- Presence of  $> 23$  natural teeth with no need for prosthetic rehabilitation

Exclusion criteria:

- Oral or systemic diseases other than periodontitis
- Mucosal / periodontal swelling or suppuration
- Pregnancy
- Minority
- Need for frequent drug consumption

Teeth with ceramic restorations and implants are excluded from analysis.

Recruitment period: September 1st to November 30th 2017

Data collection period: December 1st to March 30th 2018

*Clinical parameters*

Primary outcome measure: Plaque index by Quigley and Hein modified by Turesky et al. 1970 (T-QHI) (Turesky et al., 1970)

Secondary outcome measure: papillary bleeding index (PBI) by Saxon and Mühlemann (Saxon et al., 1977)

Both are assessed by two blinded and calibrated examiners at four sites per tooth: mesiobuccal, distobuccal, mesiolingual, and distolingual including the line angles.

*Clinical intervention*

Visit 1:

- 1) Pre-intervention: professional tooth cleaning.
- 2) Each proband is instructed by one dental hygienist with two sizes of waist-shaped test and cylindric control brushes, respectively, to guide the brushes from the buccal / labial side through the interdental spaces of all teeth four times each.
- 3) Randomization to group 1 or group 2 is performed by the toss of a coin.

First intervention period 30 days: Group 1 starts with using waist-shaped and group 2 starts with using cylindric brushes.

Visit 2:

- 1) Primary and secondary outcome parameters are measured (two calibrated blinded examiners)
- 2) Professional tooth cleaning
- 3) Re-instruction by the dental hygienist

Second intervention period 30 days: Group 2 using waist-shaped and group 1 using cylindric brushes.

Visit 3:

- 1) Primary and secondary outcome parameters are measured (two calibrated blinded examiners)
- 2) Professional tooth cleaning

In addition, probands use the electric toothbrush (Oral-B® CrossAction, Procter & Gamble, Taunus, D) with toothpaste (Colgate total original®, Colgate & Palmolive, Vienna, AT) and are instructed not to use any chemical oral rinsing solution during the study period.

*Statistical analysis*

Sample size calculation is based on a study by Chongcharoen et al. 2012.

For descriptive analysis, median and interquartile range are given. The mode is defined as the T-QHI and PBI grade most often measured in an individual. On the site level, T-QHI is converted into a dichotomous index, and the odds ratio and confidence interval (CI) for establishing plaque free interdental sites are calculated with logistic regression analysis with a significance level of  $p < 0.05$ .

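### No between-brush estimate is planned for PBI, the only secondary outcome, and its stated summaries are likely to sit at or near 0 under both brushes

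*Combined protocol and SAP*

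**What the plan says.** Under Clinical parameters the protocol lists "Secondary outcome measure: papillary bleeding index (PBI"), and no other secondary outcome. Blinded examiners score it, like T-QHI, "at four sites per tooth: mesiobuccal, distobuccal, mesiolingual, and distolingual including the line angles". This happens at Visits 2 and 3, so each patient has one full set of PBI scores per brush.

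The Statistical analysis section contains two statements that reach PBI: "For descriptive analysis, median and interquartile range are given", and "The mode is defined as the T-QHI and PBI grade most often measured in an individual". The inferential part is a site-level logistic regression for T-QHI reduced to two categories, and the 0.05 level is attached to it. No test, model, effect estimate or interval is given for PBI. The section does not say whether the median and interquartile range are taken over sites, over individual modes or over some other per-patient value.

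The inclusion criteria (Study subjects) restrict "bleeding on probing" to below 10% and allow none at sites of 4 mm or deeper. Under Clinical intervention, each period is preceded by professional cleaning and instruction by the hygienist.

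**The concern.** A median, a quartile and a mode respond poorly when most observations share the lowest value. The entry criteria select patients with little bleeding, and both periods start from a cleaned mouth, so most PBI scores may well be 0 under either brush. The likely printed result would then be 0 (0–0) against 0 (0–0), which a reader could take as no difference even if one brush left appreciably more bleeding sites than the other.

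There is also a gap that does not depend on the amount of bleeding. A crossover gives every patient a PBI value under each brush, and the plan never takes the within-patient difference. What is at stake is whether the trial says anything usable about bleeding. The primary plaque analysis is not affected.

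**Working it through.** The documents state no PBI level, effect or power, and 20 patients is justified only by a cited outside study, so there is no planned figure to reproduce. The check asks when the stated summaries would leave 0, and what a paired summary could show instead.

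**Inputs**
- Teeth: more than 23, so at least 24 (Study subjects). Sites: 4 per tooth (Clinical parameters). 24 × 4 = 96 sites per patient and visit. Teeth excluded from analysis can lower this.
- Patients: 20, so 20 × 96 = 1,920 sites per brush.
- Entry bleeding below 10%. If it was counted at the same four sites per tooth (not stated), 0.10 × 96 = 9.6, so at most 9 sites. If it was counted at six sites per tooth and all bleeding was interproximal (assumption), the share among PBI sites could reach 10% × 6/4 = 15%.

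**Step 1: thresholds**
- Individual mode: if more than 48 of 96 sites score 0, no other grade can be more frequent, so the mode is 0.
- Median over sites: leaves 0 at about 48 or 49 of 96 bleeding sites (50%), depending on the quantile convention.
- Upper quartile over sites: leaves 0 at about 24 or 25 of 96 (25%).

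**Step 2: chance per patient.** Let X be the number of bleeding sites, binomial with 96 trials and share p (sites independent, an assumption). The upper quartile is above 0 if X ≥ 25, and the median if X ≥ 49.

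| Share of bleeding sites p | P(upper quartile > 0) | P(median > 0) |
|---|---|---|
| just under 10% | 0.00001 | about 0 |
| 15% | 0.003 | about 0 |
| 20% | 0.09 | about 0 |
| 25% | 0.45 | about 0 |
| 30% | 0.83 | 0.00001 |
| 40% | 0.9985 | 0.018 |
| 50% | 1.00 | 0.46 |
| 55% | 1.00 | 0.81 |

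Suppose 8% of sites bleed with one brush and 20% with the other. At 20%, about 20 × 0.09 = 1.8 patients would have a non-zero upper quartile, and medians and modes would stay at 0. Pooled over 1,920 sites, the upper quartile stays at 0 until the overall share reaches about 25%. The contrast would very probably not show.

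**Step 3: what a paired per-patient summary could show.** One thousand simulated crossovers were run with 20 patients and 96 sites each. The logit SD was 0.5 between patients and 0.3 within patients per period, with no period effect. A paired Wilcoxon test was applied to each patient's share of bleeding sites. All rates and SDs are assumed.

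| Bleeding shares | Power | Median of per-patient shares |
|---|---|---|
| 10% vs 5% | 0.99 | about 10% vs 5% |
| 8% vs 4% | 0.99 | about 8% vs 4% |
| 15% vs 10% | 0.89 | about 15% vs 10% |

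**Step 4: precision, illustration only.** The 95% half-width for a mean within-patient difference is t(0.975, 19) × SD / √20.
- SD 5 points: 2.093 × 5 / 4.472 = 2.34 points.
- SD 10 points: 2.093 × 10 / 4.472 = 4.68 points.

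The documents give no SD, so these values do not predict this trial's precision.

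**The case against.** The strongest reply is that the floor is not established. The 10% limit concerns a different index, applies at entry, and does not bound PBI after 30 days of brush use. The documents give neither the PBI grading nor expected PBI levels in maintenance patients, so the link from entry bleeding to later PBI is an assumption. The unit of the median and interquartile range is also open: over per-patient means or shares they could differ visibly between brushes, as Step 3 shows. Finally, the null hypothesis in the Rationale concerns plaque only, and describing a secondary outcome without a test is a legitimate choice in 20 patients.

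Most of this stands as a limit on wording. A reader might infer that the PBI summaries are bound to be 0 and that the outcome cannot show a difference. The documents do not support that: if 25% to 30% of sites bled at Visits 2 and 3, the upper quartile would leave 0 in 45% to 83% of patients.

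It does not remove the point. The mode is the only per-patient PBI quantity the plan defines, and it is the summary most firmly held at 0. Per-patient means or shares are not mentioned. A descriptive secondary outcome still needs a summary able to move and an estimate of the contrast the trial was designed to make, and the absence of that estimate holds whatever the bleeding level.

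**Conclusion.** Two parts with different certainty.

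- **Certain from the text:** the plan states no between-brush estimate for PBI, does not use the within-patient pairing for it, and does not state the unit of its median and interquartile range.
- **Likely, not certain:** the stated summaries will be at or near 0 under both brushes and may hide a real difference in bleeding frequency. This rests on PBI above 0 after 30 days being roughly as frequent as bleeding on probing at entry, and on the median and quartiles being taken over sites or over individual modes. The calculation also treats sites as independent and uses 96 sites. Clustering and excluded teeth would shift the probabilities but not the conclusion.

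Bleeding would have to rise to about two and a half times the entry limit (25% against 10%) before a site-level upper quartile typically left 0, and to about five times (50%) before the median did. The change is worth making because it is nearly free, but it concerns the secondary outcome only.

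**What to change.** In the Statistical analysis section:

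- For each patient and period, compute the percentage of analysed sites with PBI above 0 and the mean PBI.
- Report the within-patient difference, waist-shaped minus cylindric, with a 95% CI from a patient-level paired analysis with a period term. Label it secondary, with no separate alpha claim.
- Keep the median, interquartile range and mode as description, and state whether each is taken over sites or over patients.

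The cost is a sentence or two of text, minor programming and one extra secondary estimate to report. It uses data already due to be collected, and eligibility, visits and the primary analysis are unchanged.

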### *Study design*

Randomized-controlled by toss of a coin

Single-blind: Two calibrated examiners

Crossover: Two intervention periods of 30 days each; wash out period one week

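### The plan's only significance test is a site-level logistic regression that treats about 4,000 correlated site scores as independent, although only 20 patients are randomised and crossed over.

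*Combined protocol and SAP*

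**What the plan says.** The Statistical analysis section gives descriptive summaries (medians with interquartile ranges, and a per-patient mode) and then its single inferential step: "On the site level, T-QHI is converted into a dichotomous index, and the odds ratio and confidence interval (CI" for a plaque-free interdental site, which "are calculated with logistic regression analysis" at a 5% significance level. It names no random effect, generalised estimating equation (GEE), robust variance, conditional or matched analysis, period or sequence term, or patient-level test.

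The design sections put the experimental unit elsewhere:

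- Study subjects: "Twenty periodontal patients", with the inclusion criterion "Presence of $> 23$ natural teeth".
- Clinical intervention: "Randomization to group 1 or group 2 is performed by the toss of a coin".
- Study design: "Crossover: Two intervention periods of 30 days each; wash out period one week".
- Clinical parameters: plaque and bleeding are "assessed by two blinded and calibrated examiners at four sites per tooth".

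**The concern.** Sites are nested in teeth, teeth in a patient-period, and each patient contributes both periods. Every site scored at one visit reflects the same person's technique and compliance over the same month with the same brush. Logistic regression with no provision for this assumes independent rows, so it ignores both the within-patient clustering and the crossover pairing.

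Its standard error shrinks as sites are added. The comparison of brushes really rests on 20 within-patient differences, and scoring more sites cannot remove the variation between a patient's two months. This is the only test of the primary outcome and of the null hypothesis in the Rationale, and no patient-level test stands behind it. A significant odds ratio could therefore be reported for two equivalent brushes.

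**Working it through.** **Inputs from the documents.** 20 patients; at least 24 teeth each (more than 23 required); 4 sites per tooth; 2 periods; alpha 0.05, taken as two-sided because sidedness is not stated. The documents give no intraclass correlation (ICC), plaque-free rate or variance component, so those below are assumptions shown over a range.

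**Step 1: rows in the model.** Patients × teeth × sites × periods:

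- 24 teeth: 20 × 24 × 4 × 2 = 3,840
- 28 teeth: 20 × 28 × 4 × 2 = 4,480

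These are site-observations. Distinct sites are half as many (1,920 to 2,240), and fewer once implants and ceramic-restored teeth are left out. If both examiners' scores were entered as separate rows, the counts would double to 7,680 to 8,960.

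**Step 2: closed-form approximation.** Let m = 24 × 4 = 96 sites per patient-period. Let ρ be the correlation among sites in the same patient-period beyond the constant patient effect, which cancels between the two brushes. The variance is understated by about DE = 1 + (m − 1)ρ, and the true error rate is 2 × [1 − Φ(1.96/√DE)].

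| ρ (assumed) | DE | SE too small by a factor of | Effective rows of 3,840 | True type I error |
|---|---|---|---|---|
| 0.01 | 1 + 95 × 0.01 = 1.95 | 1.40 | 1,969 | 16% |
| 0.02 | 2.90 | 1.70 | 1,324 | 25% |
| 0.05 | 5.75 | 2.40 | 668 | 41% |
| 0.10 | 10.5 | 3.24 | 366 | 55% |

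This slightly overstates the problem. The constant patient effect inflates the naive variance without affecting the within-patient contrast, which would lower DE a little. The simulations include it.

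**Step 3: null simulations, brushes identical.** Two sets of assumptions were used, with SDs on the logit scale:

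- Set A: 96 sites per patient-period, plaque-free probability 0.30 at the median, patient SD 1; 10,000 replicates.
- Set B: 26 teeth × 4 sites, about 40% plaque-free, patient SD 0.8, tooth SD 0.5; 3,000 to 4,000 replicates.

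| Patient-by-period SD | Naive test, A | Naive test, B |
|---|---|---|
| 0 | 3.6% | 4% |
| 0.1 | not run | 5.5% |
| 0.2 | 11% | 12% |
| 0.3 | 19% | 21% |
| 0.5 | 36% | 39% |
| 0.8 | 53% | 55% |

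**Step 4: analyses that respect the patient.** Across all set A scenarios, a paired t-test on patient proportions, and the same odds ratio with a patient-clustered robust variance (factor 20/19) and t on 19 df, gave 4.6% to 5.3%. Under set B the two stayed within 4.5% to 5.7%. A Mantel-Haenszel test stratified by patient did not repair the problem under set B: 24% at SD 0.3 and 42% at SD 0.5. Adjusting for the patient alone leaves patient-by-period variation in place.

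**Step 5: what SD 0.3 means.** Starting from 38% plaque-free (logit −0.49), one SD up gives about 45% and one SD down about 31%. The difference between a patient's two periods has SD 0.3 × √2 = 0.42 logits, or about 0.38 × 0.62 × 0.42 = 10 percentage points.

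**The case against.** The plan never says that sites are treated as independent. Mixed, GEE and conditional models are all logistic regressions, and an unwritten adjustment may have been intended. That is a fair reading of intent, but it does not rescue the text: nothing else in the documents handles the correlation, and an analyst who ran the unadjusted model would be following the plan.

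The size of the error rests on assumed variances. This stands. The figures run from slightly conservative to more than half of null trials, and an SD of 0.3 is not trivial variation (about 10 points between periods). Even so, no variation at all between two months of self-performed cleaning is the least plausible case, and neither direction of error delivers the nominal 5%.

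The documents do not say that both examiners score every site or that both scores enter as rows. The doubled-row figures are therefore conditional: under set B with perfect agreement, 37% at SD 0.3 and 55% at SD 0.5. The finding does not need them.

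The simulations support the paired analysis and the clustered robust logistic test. A mixed logistic model with several random effects was not simulated, and the evidence that a patient effect alone is insufficient comes from the stratified test rather than from a fitted random-intercept model.

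**Conclusion.** The concern holds. Followed as written, the sole inferential analysis uses the wrong unit, and its confidence interval and p-value are invalid. That conclusion needs no assumption beyond the design. The size does: under the assumed variances, the true error rate at a nominal 5% is about 11% to 12% for a patient-by-period SD of 0.2, 19% to 21% at 0.3, 36% to 39% at 0.5 and 53% to 55% at 0.8. It is close to nominal at 0.1 and slightly below it at zero. Because no other test addresses the primary outcome, this must be corrected before the result can be interpreted.

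**What to change.** Rewrite the inferential part of the Statistical analysis section so that the patient is the unit of inference:

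- Keep the odds ratio for a plaque-free site, but estimate it by GEE logistic regression clustered on patient, with brush and period terms, a small-sample-corrected robust variance and a t reference based on the number of patients.
- Alternatively, use a mixed logistic model with random effects for patient, patient-by-period and tooth. A patient intercept alone should not be relied on.
- Confirm with a paired, period-adjusted patient-level analysis of the proportion of plaque-free sites.
- State how the two examiners' scores are combined before analysis. If they are averaged, define plaque-free explicitly, for example as an average of 0, so that half grades are not left undefined.

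The cost is a few sentences and a few lines of code. No new data or design change is needed. The drawback is that the interval will usually be wider than the naive one.

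### With no patient term and no both-visits rule, patients lost after Visit 2 make part of the brush odds ratio a between-patient comparison and raise its false-positive rate

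*Combined protocol and SAP*

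**What the plan says.** The trial enrols "Twenty periodontal patients of the University Hospital of Dental Prosthetics and Restorative Dentistry" (Study subjects) in a two-period design: "Crossover: Two intervention periods of 30 days each; wash out period one week" (Study design). Order of use is set by chance: "Randomization to group 1 or group 2 is performed by the toss of a coin" (Clinical intervention, Visit 1), so group sizes are not forced to be equal.

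Visit 1 lists cleaning, instruction and allocation but no outcome assessment. Visits 2 and 3 each carry the item "Primary and secondary outcome parameters are measured (two calibrated blinded examiners". Scoring is done "at four sites per tooth: mesiobuccal, distobuccal, mesiolingual, and distolingual including the line angles" (Clinical parameters). Each patient therefore yields one set of scores per brush.

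Under Statistical analysis the plan states: "On the site level, T-QHI is converted into a dichotomous index, and the odds ratio and confidence interval (CI" are obtained by logistic regression at the 0.05 level. It names no patient, pairing, period or sequence term, no analysis set, and no handling of withdrawals. The one rule on what enters the analysis concerns teeth: "Teeth with ceramic restorations and implants are excluded from analysis" (Study subjects).

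**The concern.** A crossover earns its efficiency by comparing each patient with himself or herself. That holds in a site-level regression without a patient term only while every patient contributes the same sites to both brushes. Then differences in cleaning skill cancel, because each patient's level enters both sides equally.

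Losing Visit 3 breaks the balance. From the assignment "Second intervention period 30 days: Group 2 using waist-shaped and group 1 using cylindric brushes", a Group 1 patient who stops after Visit 2 is seen only with the waist-shaped brush, and a Group 2 patient only with the cylindric brush. All of that patient's sites then sit on one side of the odds ratio, and the patient's general plaque level is counted as if it belonged to the brush. With 20 patients, two such losses are 10% of the sample, and this odds ratio is the trial's only planned inferential result.

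**Working it through.** **Inputs from the protocol.** 20 patients; more than 23 natural teeth, so at least 24 × 4 = 96 sites per visit before tooth exclusions; significance level 0.05 (two-sided assumed).

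**Assumed, because the protocol gives none.** A true odds ratio (OR) of 1, 96 analysed sites per patient, the number of dropouts, plaque-free rates, between-patient SD, no period effect and no patient-by-brush interaction.

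There is no plan figure to reproduce. The sample size is referred to an earlier study, with no effect size, variability, power or dropout allowance.

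**1. Fixed example, all losses from Group 2.** Completers are plaque-free at 50% of sites under both brushes; d patients with rate p have cylindric data only. An unadjusted logistic regression on brush gives the 2×2 odds ratio, with SE(log OR) = √(sum of the reciprocals of the four cells).

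For d = 2, p = 0.10:
- Waist-shaped: 18 × 96 = 1,728 sites, 864 plaque-free, odds 1.
- Cylindric: 1,920 sites, 864 + 19.2 = 883.2 plaque-free (46%), odds 883.2/1,036.8 = 0.852.
- OR = 1/0.852 = 1.174; log OR = 0.160.
- SE = √(1/864 + 1/864 + 1/883.2 + 1/1,036.8) = 0.0664; z = 2.41; 95% CI 1.031 to 1.337.

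| Lost, one sequence | p = 0.10 | p = 0.20 |
|---|---|---|
| 1 | 1.083 (0.953–1.232) | 1.062 (0.934–1.207) |
| 2 | 1.174 (1.031–1.337) | 1.128 (0.990–1.284) |
| 3 | 1.273 (1.115–1.453) | 1.198 (1.049–1.367) |

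One similar loss in each sequence gives OR 1.00.

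**2. Simulation, true OR 1.** 4,000 runs per setting, with a patient intercept on the logit scale, median plaque-free rate 50%, and coin-toss allocation (runs with fewer than 4 or more than 16 in a group set aside). False-positive rate of the unadjusted site-level analysis:

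| Missing Visit 3 | SD 0.5 | SD 1.0 | SD 1.5 | Mean OR |
|---|---|---|---|---|
| None | 0.042 | 0.032 | 0.024 | 1.00 |
| 2 at random | 0.074 | 0.137 | 0.198 | 1.00 |
| 2 worst-plaque, either group | 0.161 | 0.300 | 0.404 | 1.00 |
| 2 worst-plaque, Group 2 only | 0.174 | 0.426 | 0.629 | 1.07 / 1.12 / 1.16 |

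With no losses the test does not over-reject. The inflation comes from the one-brush records.

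**3. Same data, compared within patient.** Using only patients with both visits (paired t-test on patient proportions for the rejection rate), the mean OR was 1.00 and the false-positive rate 0.043 to 0.054 in every setting. Adding a patient effect to the examples in step 1 also returns a brush OR of 1.00.

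**4. Single teeth.** One tooth with four plaque-covered sites missing on one brush: waist-shaped 958/1,916, cylindric 958/1,920, OR = 962/958 = 1.004. Ten such teeth, all on the same brush: OR = 980/940 = 1.04 (0.92 to 1.18).

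**The case against.** The strongest reply is that the plan never says the regression is unadjusted. It is brief, and a model matched on site or containing a patient effect would remove the mechanism. This is true, and if such a model is intended, writing it down settles the point. As the text stands, a site-level logistic regression with no further terms is the plain reading.

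A second reply is that this is largely the clustering problem again. Much of that stands. The nominal significance in the fixed examples rests on a standard error that ignores clustering: with patient-clustered errors, z falls from 2.41 to 1.45 (two lost at 10%) and from 2.68 to 1.82 (three lost at 20%). With two random losses, clustered errors bring the false-positive rate to about 0.02 to 0.06, depending on the small-sample form used. A clustered error does not, however, move a shifted point estimate, and the plan provides neither remedy.

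Several stronger readings are tempting and are not supported:
- *Missing Visit 3 data bias the odds ratio.* A reader might infer this from the one-sequence examples. On average it does not happen unless losses depend on both sequence and plaque level. Under coin-toss allocation, two unrelated dropouts share a sequence only half the time and three a quarter of the time.
- *A lost or newly restored tooth does the same.* The effect is negligible, and the exclusion of ceramic-restored teeth reads as removing the tooth altogether, not one visit's record.
- *Each dropout contributes at least 96 sites.* Tooth exclusions can take the analysed number below 96.
- *Restricting to complete pairs cures the problem.* The OR of 1.00 in the fixed examples holds by construction. If patients stop because of how they responded to the first brush, the completers are themselves a selected group.

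**Conclusion.** The concern holds as a gap in the planned analysis. It does not show that the result will be biased. Under the plain reading, any patient lost after Visit 2 brings between-patient variation into the brush comparison. Two losses unrelated to brush or plaque are enough to take the false-positive rate from below 0.05 to about 0.07 to 0.20, with the average OR unchanged at 1.00. A systematic shift, of the order of 1.13 to 1.17 for two patients at 20% to 10% plaque-free against 50%, needs both to come from the same sequence and to differ from the rest in plaque level.

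These sizes rest wholly on the assumptions listed above. If nobody misses Visit 3, the problem does not arise.

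**What to change.** Under Statistical analysis, state that the brush odds ratio is estimated within patient. Either of two forms would do:
- logistic regression with a patient effect and patient-level (clustered) inference; or
- restriction to sites scored at both Visit 2 and Visit 3, again with inference at patient level.

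Either way, one-visit patients no longer drive the comparison. Also report the number of patients scored at one visit only, by sequence, brush in use and reason for stopping, and describe the medians and modes of both indices on the same patients for both brushes.

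The cost is a few sentences, with no added visits or staff. One-visit records will add little or nothing to the main comparison, but they hold little within-patient information on the brush difference. Neither form removes bias if stopping depends on the patient's response to the first brush, which is why the reasons for stopping should be reported.
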